12.3.1.5 Determination of subjects for analysis

Only those subjects that have completed both a baseline and 6-month 48 hour ambulatory ECG monitor or are 6-month effectiveness failures based on other criteria will be included in the main analysis cohort for this objective.

In the event that the recording duration of the ambulatory ECG monitor exceeds 48 hours (e.g. a 7 day ECG patch monitor is used), the AF burden will be computed by the core laboratory for the initial 48 hours only.

Likewise, in the event the ambulatory ECG monitor is less than 48 hours (e.g. due to inadequate ECG patch monitor fixation, subject compliance) the AF burden will be determined by the core laboratory based on the total usable or analyzable recording period. Subjects may be asked to repeat an ambulatory ECG monitoring session if less than 24 hours of analyzable monitoring time is obtained. Subjects with less than 24 hours of usable ambulatory ECG recording time will be considered missing in the analysis (unless they are 6-month effectiveness failures based on other criteria) and included in sensitivity analyses as described below.

12.3.1.6 Confidence Interval Width

The 6-month effectiveness rate among all 138 subjects randomized to the ablation management arm in TTOP-AF was 55.8% (77/138; 95% CI: 47.1% - 64.2%). However, in this intention-to-treat analysis, 17 subjects missing their 6-month ambulatory ECG monitor assessment were included in the analysis as failures. If only subjects with 6-month ambulatory ECG monitor data available in TTOP-AF were included in the analysis (the analogous analysis cohort in this study) the 6-month effectiveness rate was 63.6% (77/121; 95% CI: 54.4% - 72.2%). However, the TTOP-AF protocol required amiodarone be discontinued 28 days prior to the 6-month visit, did not require discontinuation of other antiarrhythmic drugs or DC cardioversions until 5 days prior to the 6-month ambulatory ECG monitor assessment. Thus, while it is expected that the estimated 6-month effectiveness rate in this study will be greater than 50%, it may be less than 64% due to differences in allowed concomitant therapy use between studies.

Based on the following assumptions:

- Up to 420 subjects will be enrolled
- 300 subjects are required to complete the 30-day post-ablation visit and have the opportunity for a reablation procedure (i.e. complete 6-month visit)

or complete the 30-day post-reablation visit if a reablation procedure is required

- Total of 55 study centers activated
- 14 months to activate the 55 centers
- Enrollment rate of 0.4 subjects per center per month once activated
- 30% of subjects will be re-ablated prior to their 6-month visit
- 10% annualized attrition rate

It was estimated via a simulation study that approximately 284 subjects would complete the 6-month ambulatory ECG monitor assessment. Assuming 200 subjects have evaluable baseline and 6-month ambulatory ECG monitor data and the observed 6-month effectiveness rate is 55%, then the exact 95% two-sided confidence interval should have a width no larger than 14.2% with a lower limit of at least 47.8%. Similarly, if the observed 6-month effectiveness rate is 50%, the confidence interval width should be no greater than 14.3% with a lower limit of at least 42.9%.

12.3.1.7 **Missing data**

Subjects will only be included in this analysis for the 6-month effectiveness objective if they have both a baseline and 6-month 48-hour ambulatory ECG monitor that are readable by the core lab or are missing a 48-hour ambulatory ECG monitor data and 6-month effectiveness failures based on other criteria at the time of the visit cutoff date. However, should the issue of missing data arise; all ablated subjects that complete the 6-month visit at the time of the visit cutoff regardless of ambulatory ECG monitor data status will be included in a tipping point analysis to evaluate the impact of missing data. Specifically, subjects completing the 6-month study visit but missing the ambulatory ECG monitor assessment who are not 6-month effectiveness failures based on other criteria will be included as successes and then iteratively included as failures in the tipping point analysis.

12.3.2 *Secondary Objective #2: Acute procedural success*

12.3.2.1 **Objective**

Confirm acute post-procedural effectiveness.

12.3.2.2 **Hypothesis**

There is no pre-specified hypothesis associated with this secondary objective.

12.3.2.3 **Definition acute procedural success**

Acute procedural success is defined as meeting all four of the following conditions:

1. Only Phased RF catheters used in the left atrium to achieve procedure success AND
2. All accessible pulmonary veins were isolated (entrance block)
3. CFAEs and high frequency intracardiac electrogram amplitudes were mapped and ablated as necessary with Phased RF System

4. Sinus rhythm is restored at the end of the ablation procedure (with or without cardioversion)

12.3.2.4 **Analysis Methods**

All ablation procedure parameters will be captured on the case report forms. For estimating the acute success rate, all subjects with an attempted ablation where at least one of the Phased RF catheters were deployed into the left atrium will be included in the denominator. The numerator will include all subjects in the denominator who met all the conditions for acute procedural success defined above. A two-sided lower 95% exact confidence interval for the acute procedural success rate will be calculated. Subjects that have a reablation attempt will be considered acutely successful if they meet all the conditions for their index procedure and conditions 1 and 4 of the acute success definition for their reablation attempt since the source of recurrent AF will be unknown.

In addition to calculating the acute success rate on a per subject basis, the acute success rate will be calculated on a per procedure basis. The denominator for the per procedure rate will be all Phased RF procedures where at least one Phased RF catheter was deployed into the left atrium. The numerator will be all Phased RF procedures in the denominator that meet all four conditions of the acute success definition. A two-sided 95% two-sided confidence interval for this rate will also be calculated using the method of Rao and Scott for clustered binary data since subjects may have up to two ablation procedures.

12.3.2.5 **Determination of subjects for analysis**

All ablation procedures that meet the cutoff date for the analysis of the primary objective where at least one Phased RF catheter was deployed into the left atrium will be included in the analysis.

12.3.2.6 **Missing data**

There is not expected to be any missing data associated with the analysis of this objective since the objective is evaluated at the time of the procedure.

12.3.3 *Secondary Objective #3: Pulmonary Vein Stenosis*

12.3.3.1 **Objective**

Characterize the incidence of PVS 3 months post ablation procedure as determined by MRI or CT scan.

12.3.3.2 **Hypothesis**

There is no pre-specified hypothesis associated with this secondary objective.

12.3.3.3 **Definition of pulmonary vein stenosis**

Pulmonary vein stenosis will be defined as: a greater than 70% reduction in the baseline luminal diameter.

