12.2.6 Sample size and power

[figure not shown]
A sample size of 300 subjects completing the 30-day post procedure follow-up visit and having the opportunity for a reablation procedure (i.e. completing the 6-month follow-up visit) or having a reablation procedure and completing the 30-day post-reablation visit provides at least 80% power to test the primary study hypothesis given the following assumptions:

1. One-sided type I error rate of 0.05
2. Exact test of a binomial proportion versus a fixed performance goal of 3.5%
3. Observed stroke rate must be less than 1.8%.
4. Assumed true stroke rate is 1.3%

Figure 1 displays the power of the study to meet its primary objective when the true stroke rate ranges from 0.1% to 3.5% and 300 subjects complete the 30-day post-ablation (or reablation) visit and have had the opportunity for a reablation procedure. Specifically, the study has 90% power if the true stroke rate is 1%, 80% power if the true stroke rate is 1.3%, and 55% power if the true stroke rate is 1.8%. Figure 1 also demonstrates that the type I error is less than 5% when the true stroke rate is 3.5%.

Assuming an annualized attrition rate of 10% following the index ablation procedure, a uniform reablation rate of 30% within 180 days of the index ablation procedure, and a conservative 26% pre-procedure attrition rate up to 420 enrolled subjects will be required to ensure that at least 300 subjects complete the 30-day post ablation follow-up visit and have the opportunity for a reablation procedure or have a reablation procedure and complete the 30-day post-reablation procedure visit. Note that it is not anticipated that all 420 subject enrollments will be required, since study enrollment will cease once enough subjects have completed an index Phased RF procedure to ensure that the target sample size of 300 evaluable subjects can be obtained.

Figure 1: Study Power versus True Stroke Rate

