12.3.1.4 Analysis Methods

Acute effectiveness for each subject will be determined as described in section 12.3.2. In order for a subject to meet the acute procedural success criterion for the 6-month effectiveness endpoint, the subject must be an acute procedural success for their index and reablation procedure (if required). Ambulatory ECG monitor recordings will be completed at the baseline and 6-month post final Phased RF ablation visit. Ambulatory ECG recordings will be read and summarized by the Holter core laboratory. For the baseline and 6-month post-ablation procedure ambulatory ECG recording, the percentage of time in clinically significant AF (AF > 10 minutes) will be calculated as the total number of seconds in clinically significant AF divided by the total analyzable ambulatory ECG monitor recording time in seconds. The percent reduction from baseline will be calculated as the difference of the percentage of time in clinically significant AF between the baseline and 6-month post-ablation procedure visit divided by the percentage of clinically significant AF at baseline. Subjects with at least a 90% reduction in clinically significant AF will be considered successful for the ambulatory ECG component of 6-month effectiveness endpoint. Adjustments to all cardiovascular medications including antiarrhythmic drugs and dates of all DC Cardioversions will be captured on the case report forms.

Only those subjects that have a baseline and 6-month post-procedure 48-hour ambulatory ECG monitor data that are readable by the core lab or are missing ambulatory ECG data but were 6-month effectiveness failures based on other criteria at the time of the visit cutoff date will be included in the analysis of this

objective. Specifically, the denominator for the 6-month effectiveness rate will include all subjects that had at least one Phased RF ablation procedure where an investigational catheter was deployed into the left atrium and have baseline and 6-month ambulatory ECG monitor data available or do not have ambulatory ECG data available but were 6-month effectiveness failures based on other criteria. The numerator will include all subjects in the denominator that meet all four 6-month effectiveness conditions. A two-sided 95% exact confidence interval for 6-month effectiveness rate will be calculated.

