12.3.3.7 Missing data

Subjects missing both a readable baseline and 3-month follow-up MRI or CT-scan will not be included in the main analysis cohort for this objective. However, should the issue of missing data arise; all subjects randomized to the PVS assessment cohort with at least one Phased RF catheter deployed in the left atrium will be included in a tipping point analysis regardless of whether MRI or CT-scans are available. Specifically, subjects randomized to this cohort, but missing an evaluable 3-month MRI or CT-scan will be included as PVS negative and iteratively added as PVS positive in the tipping point analysis.

[REDACTED]

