### **3.3.1.6 Missing Data**

Subjects will only be included in this analysis for the 6-month effectiveness objective if they have both a baseline and 6-month 48-hour Holter that are readable by the core lab or are missing a 48-hour Holter data and are 6-month effectiveness failures based on other criteria at the time of the visit cutoff date. However, should the issue of missing data arise, all ablated subjects that complete the 6-month visit at the time of the visit cutoff regardless of Holter data status will be included in a tipping point analysis to evaluate the impact of missing data. Specifically, subjects completing the 6-month study visit but missing the Holter assessment who are not 6-month effectiveness failures based on other criteria will be included as successes and then iteratively included as failures in the tipping point analysis.

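### The tipping-point analysis for 6-month effectiveness leaves out ablated subjects who exit before the 6-month visit without a known failure

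*Protocol*

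**What the plan says.** Protocol 12.3.1.4, 12.3.1.5 and 12.3.1.7 define the main analysis set. It holds ablated subjects with readable baseline and 6-month ambulatory ECGs, plus those who "are missing ambulatory ECG data but were 6-month effectiveness failures based on other criteria at the time of the visit cutoff date". The second group counts as failures.

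Protocol 12.3.1.7 then sets the population for the sensitivity analysis: "all ablated subjects that complete the 6-month visit at the time of the visit cutoff", whether or not they have ECG data. Its next sentence says whose outcome is varied from success to failure: "subjects completing the 6-month study visit but missing the ambulatory ECG monitor assessment who are not 6-month effectiveness failures based on other criteria". SAP 3.3.1.6 carries the same restriction: "all ablated subjects that complete the 6-month visit at the time of the visit cutoff regardless of Holter data status will be included".

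The plan's other tipping points have no such condition. Protocol 12.2.8 and SAP 3.2.6 apply one to subjects who leave before the 30-day visit, and another to those who leave after it but before the reablation period ends. For pulmonary vein stenosis, protocol 12.3.3.7 takes in "all subjects randomized to the PVS assessment cohort with at least one Phased RF catheter deployed in the left atrium", with or without a scan.

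**The concern.** The analysis is meant to show how far missing data could move the 6-month effectiveness rate. A subject who leaves the study has no 6-month ECG, just as a subject who attends without a usable recording has none, but only the second is varied. No reason is given for the difference, and it departs from the approach taken for the other two endpoints.

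The direction of any bias is unknown. Early leavers can enter the main analysis only as failures, because success needs a 6-month ECG. Omitting the rest could make the rate too low. If subjects leave because AF has returned, omitting them could make it too high. That is why both extremes should be shown.

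What is at stake is how a reader takes the reported range. If it is presented as covering the missing data, it will look complete when one identifiable group is absent.

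**Working it through.** **Reproducing the plan's figures.** The exact (Clopper-Pearson) two-sided 95% interval for 110/200 is 47.8% to 62.0%, width 14.2 points. For 100/200 it is 42.9% to 57.1%, width 14.3. The prior-study figures, 77/138 = 55.8% (47.1% to 64.2%) and 77/121 = 63.6% (54.4% to 72.2%), also reproduce. All agree with protocol 12.3.1.6.

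**Who is in which analysis (ablated subjects).**

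| Status | Main analysis | Tipping point |
|---|---|---|
| Readable baseline and 6-month ECG | yes | yes, fixed |
| No usable ECG, failed another criterion | yes, as failure | fixed, not varied |
| Attended 6-month visit, no usable ECG, no known failure | no | yes, varied |
| Exited before 6-month visit, no known failure | no | no |

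The last row is the gap.

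**How many subjects.** Protocol 12.2.6 plans for "a conservative 26% pre-procedure attrition rate up to 420 enrolled subjects will be required", so the number ablated is at most 420 × (1 − 0.26) = 310.8.

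*Route A, attrition model.* The inputs are 10% annual attrition and 30% reablation, uniform over 180 days (12.2.6), with the 6-month clock restarting at reablation (7.6). With hazard h = −ln(0.9) = 0.105 per year and T = 180/365.25 = 0.493 years:

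- P(reach final 6-month visit) = e^(−hT) × [0.7 + 0.3 × (1 − e^(−hT))/(hT)] = 0.949 × [0.7 + 0.3 × 0.974] = 0.942
- Early exits = 310.8 × (1 − 0.942) = about 18

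Taking the hazard as 0.10, or the visit at day 210 (the window end), gives about 17 to 21.

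*Route B, the protocol's own simulation.* Protocol 12.3.1.6 expects about 284 subjects to complete the 6-month ECG, and 310.8 − 284 = about 27. The simulation's full inputs are not given. The 27 may include subjects not yet due at the cutoff, so I treat it as the upper figure.

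The SAP's planning values differ (350 enrolled, 11% pre-procedure attrition, 275 completers) and would give 350 × 0.89 − 275 = 36.5. I use the protocol's values throughout.

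**Effect on the rate**, if none of the early exits is already a known failure:

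| Base | Exits added | All failures | All successes |
|---|---|---|---|
| 110/200 = 55.0% | 18 | 110/218 = 50.5% | 128/218 = 58.7% |
| 110/200 = 55.0% | 27 | 110/227 = 48.5% | 137/227 = 60.4% |
| 156/284 = 54.9% | 18 | 156/302 = 51.7% | 174/302 = 57.6% |
| 156/284 = 54.9% | 27 | 156/311 = 50.2% | 183/311 = 58.8% |

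**Compared with what is already planned.** Suppose all 284 − 200 = 84 remaining completers lacked a usable ECG. The planned tipping point would span 110/284 = 38.7% to 194/284 = 68.3%. Adding 18 exits widens this to 110/302 = 36.4% and 212/302 = 70.2%. Adding 27 gives 110/311 = 35.4% and 221/311 = 71.1%. Each extreme moves by about 2 to 3 points.

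**The case against.** The case for leaving the text alone is that the consequence is small. Section 12 of the protocol ties study success to the primary objective alone, and 12.3.1.2 gives this objective no hypothesis. Its stated purpose is to show that investigators were not overly cautious, so there is no decision to tip. With 18 exits, the range of 50.5% to 58.7% lies inside the interval the plan already accepts (47.8% to 62.0%). This stands, and it limits the weight of the point.

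Restricting the set to visit completers also does something useful. The 6-month ECG is timed from the final ablation, while the cutoff in protocol 12.2.10 and SAP 3.1.4.1 requires only the 30-day visit after reablation. Subjects reablated late may be in follow-up at the cutoff with no 6-month ECG because none is due. Adding everyone without an ECG would treat them as missing. This also stands, and it shapes the fix. It does not justify dropping subjects who have left.

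A reader might infer that all early dropouts are ignored. They are not: those who failed another criterion, such as acute procedural success, count as failures in the main analysis.

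A reader might also infer that early exits are the main source of missing data, or the source most related to outcome. The documents show neither. Planning figures allow up to 84 completers without a usable ECG, against 18 to 27 exits. The 84 looks like a cautious planning margin rather than a forecast, so the documents do not settle which group will be larger.

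Nor is 50% a threshold. Protocol 12.3.1.6 states it as an expectation, not a criterion.

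**Conclusion.** The gap is in both documents: early exits without a known failure enter neither analysis. The missing-data text is readable in both and agrees. Text redacted after SAP 3.3.1.3 could hold more, but nothing readable brings these subjects in.

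The size is modest. At most about 18 to 27 of about 311 ablated subjects are affected, moving a rate of 55.0% by roughly 4 to 7 points at either extreme on the 200-subject base, or by 2 to 3 points beyond a planned tipping point that already had 84 unknowns. These are upper values, because some early exits will already be known failures. They rest on the protocol's enrolment, attrition and reablation assumptions.

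The prior study shows that handling can matter: counting 17 of 138 subjects without an ECG as failures, rather than excluding them, moved the rate from 63.6% to 55.8%. The documents do not say how many of those 17 had dropped out, so this illustrates sensitivity and does not predict the effect here.

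The planned analysis can understate the impact of missing data on a descriptive objective. The primary endpoint and the success rule are unaffected. The change is worth making because it is cheap and brings this analysis into line with the other two.

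**What to change.** In protocol 12.3.1.7 and SAP 3.3.1.6, define the tipping-point set as all ablated subjects who, by the visit cutoff, completed the 6-month visit, exited the study before it, or had their 6-month window after the final ablation close. Within that set, vary those who lack evaluable ECG data and are not known failures. State that subjects still in follow-up whose 6-month ECG is not yet due at the cutoff are excluded.

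The cost is one sentence in each document, minor programming to separate early exit from not yet due, and a somewhat wider reported range. No new data are needed.

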12.3.3.4 Analysis Methods

One hundred (100) subjects will be randomized to the PVS assessment cohort. Subjects randomized to the PVS assessment cohort will have a CT-scan or MRI scan at their baseline visit and a CT-scan or MRI scan for PVS assessment at their first 3-month post-ablation visit (e.g. subjects with a reablation procedure following their 3-month post index ablation assessment will not have another scan at their 3-month post reablation visit). The core laboratory's assessment of PVS status will be collected on the CRFs. For computing the PVS rate at 3 months post ablation the denominator will be all subjects that are randomized to the PVS assessment cohort, have at least one ablation procedure with one or more Phased RF catheters deployed, and have evaluable CT or MRI scans available at their baseline and 3-month follow up visits. The numerator will be all subjects included in the denominator that were classified by the core laboratory as having PVS by the core laboratory. A two-sided 95% exact confidence interval for the 3-month post-procedure PVS rate will be calculated.

12.3.3.5 Determination of subjects for analysis

Only those subjects that are randomized to the PVS assessment cohort, have at least one ablation procedure with one or more Phased RF catheters deployed in the left atrium, and have CT or MRI scans at baseline and at the 3-month follow-up visit (or 3-month post-reablation visit if subject was reablated) that are readable by the core lab will be included in the analysis of this objective.

12.3.3.6 Confidence Interval Width

The PVS rate among all 176 ablated subjects in the TTOP-AF study was 4% (7/176; 95% CI: 1.6% to 8%). Based on the added training and other mitigation strategies employed in this protocol to avoid PVS it is assumed that the true PVS rate will be 2%. If at least 80 of the 100 subjects randomized to the PVS assessment cohort have readable baseline and 3-month follow-up MRI or CT-scans and the observed PVS rate is 2% the exact 95% two-sided confidence should have a width no larger than 7.8% with an upper confidence boundary no greater than 8%.

12.3.3.7 Missing data

Subjects missing both a readable baseline and 3-month follow-up MRI or CT-scan will not be included in the main analysis cohort for this objective. However, should the issue of missing data arise; all subjects randomized to the PVS assessment cohort with at least one Phased RF catheter deployed in the left atrium will be included in a tipping point analysis regardless of whether MRI or CT-scans are available. Specifically, subjects randomized to this cohort, but missing an evaluable 3-month MRI or CT-scan will be included as PVS negative and iteratively added as PVS positive in the tipping point analysis.

[REDACTED]

